12.5.2 Safety endpoints

Full details of all planned analyses will be included in the study analysis plan. However, a brief description of the approaches used are given below.

12.5.2.1 Adverse events

All information obtained on adverse events will be displayed by treatment group and participant.

The number (and percentage) of participants with treatment emergent adverse events (events started after the first dose of study medication or events present prior to start of double-blind treatment but increased in severity based on preferred term and up to last study visit will be summarized in the following ways:

- by treatment, primary system organ class and preferred term.
- by treatment, primary system organ class, preferred term and maximum severity (based on CTCAE Version 5.0 grades).

Separate summaries will be provided for study medication related adverse events, death, serious adverse events, other significant adverse events leading to discontinuation.

The number (and proportion) of participants with adverse events of special interest (AESI) such as worsening cytopenias, infections, etc. will be summarized by treatment.

[figure not shown]
A participant with multiple adverse events within a primary system organ class is only counted once towards the total of the primary system organ class.

12.5.2.2 Vital signs

All vital signs data will be listed by treatment group, participant, and visit/time and if ranges are available, abnormalities (and relevant orthostatic changes) will be flagged. Summary statistics will be provided by treatment and visit/time.

12.5.2.3 Clinical laboratory evaluations

All laboratory data will be listed by treatment group, participant, and visit/time and if normal ranges are available abnormalities will be flagged. Summary statistics will be provided by treatment and visit/time.

[REDACTED]

12.7 Interim analyses

No interim analysis is planned. An internal Data Monitoring Committee at Novartis will be established to conduct periodic unblinded safety reviews.

12.8 Sample size calculation

12.8.1 Primary endpoint(s)

Assuming a true treatment difference in clinical failure rate of 15% for ruxolitinib added to SoC therapy compared to placebo added to SoC therapy, a sample size of approximately 402 participants provides at least 80% power that the primary analysis will be statistically significant at the two-sided 5% significance level. This holds for a variety of different assumptions with respect to clinical failure rates (Table 12-1).

These sample size assumptions were evaluated in East Version 6.4.

Table 12-1 Sensitivity of sample size assumptions to different failure rates for level of significance alpha = 0.05

Standard of care failure rate (%)	Ruxolitinib failure rate (%)	Power (%)
80	65	91
70	55	85
60	45	82
50	35	82
40	25	85
30	15	91

13 Ethical considerations and administrative procedures

13.1 Regulatory and ethical compliance

This clinical study was designed and shall be implemented, executed and reported in accordance with the ICH Harmonized Tripartite Guidelines for Good Clinical Practice, with applicable local regulations (including European Directive 2001/20/EC, US CFR 21), and with the ethical principles laid down in the Declaration of Helsinki.

(Applicable to US only) This study is being conducted to determine whether ruxolitinib can safely and effectively be used to mitigate, treat, or cure COVID-19 or limit the harm of the COVID-19 pandemic in accordance with the Secretary of the Department of Health and Human Services' (HHS's) Declaration under the Public Readiness and Emergency Preparedness Act for medical countermeasures against COVID-19 (COVID-19 Declaration) effective February 4, 2020. The purpose of this study is to test the efficacy and safety of ruxolitinib in patients with COVID-19 associated cytokine storm. This study is authorized to proceed under an approved investigational new drug application (IND) in accordance with the public health and medical response of FDA, an Authority Having Jurisdiction as described under the PREP Act, to prescribe, administer, deliver, distribute or dispense this Covered Countermeasure as defined by and following the HHS's COVID-19 Declaration.

13.2 Responsibilities of the investigator and IRB/IEC

Before initiating a trial, the investigator/institution must obtain approval/favorable opinion from the Institutional Review Board/Independent Ethics Committee (IRB/IEC) for the trial protocol, written informed consent form, consent form updates, participant recruitment procedures (e.g., advertisements) and any other written information to be provided to participants. Prior to study start, the investigator is required to sign a protocol signature page confirming his/her agreement to conduct the study in accordance with these documents and all of the instructions and procedures found in this protocol and to give access to all relevant data and records to Novartis monitors, auditors, Novartis Quality Assurance representatives, designated agents of Novartis, IRBs/IECs, and regulatory authorities as required. If an inspection of the clinical site is requested by a regulatory authority, the investigator must inform Novartis immediately that this request has been made.

13.3 Publication of study protocol and results

The protocol will be registered in a publicly accessible database such as clinicaltrials.gov and as required in EudraCT. In addition, after study completion (defined as last patient last visit) and finalization of the study report the results of this trial will be submitted for publication and posted in a publicly accessible database of clinical trial results, such as the Novartis clinical trial results website and all required Health Authority websites (e.g. Clinicaltrials.gov, EudraCT etc.).

For details on the Novartis publication policy including authorship criteria, please refer to the Novartis publication policy training materials that were provided to you at the trial investigator meetings.

13.4 Quality Control and Quality Assurance

Novartis maintains a robust Quality Management System (QMS) that includes all activities involved in quality assurance and quality control, to ensure compliance with written Standard Operating Procedures as well as applicable global/local GCP regulations and ICH Guidelines.

Audits of investigator sites, vendors, and Novartis systems are performed by auditors, independent from those involved in conducting, monitoring or performing quality control of the clinical trial. The clinical audit process uses a knowledge/risk based approach.

Audits are conducted to assess GCP compliance with global and local regulatory requirements, protocols and internal SOPs, and are performed according to written Novartis processes.

14 Protocol adherence

16.1 Appendix 1: Liver event and laboratory trigger definitions & follow-up requirements

Table 16-1 Liver event and laboratory trigger definitions

	Definition/ threshold
Liver laboratory triggers	
 ALT or AST > 5 × ULN
If ALT, AST and total bilirubin normal at baseline:	
 ALP > 2 × ULN (in the absence of known bone pathology) Total bilirubin > 3 × ULN (in the absence of known Gilbert syndrome) ALT or AST > 3 × ULN and INR > 1.5 Potential Hy's Law cases (defined as ALT or AST > 3 × ULN and Total bilirubin > 2 × ULN [mainly conjugated fraction] without notable increase in ALP to > 2 × ULN) Any clinical event of jaundice (or equivalent term) ALT or AST > 3 × ULN accompanied by (general) malaise, fatigue, abdominal pain, nausea, or vomiting, or rash with eosinophilia Any adverse event potentially indicative of a liver toxicity*
If ALT or AST abnormal at baseline:	
 ALT or AST > 2x baseline or > 300 U/L (whichever occurs first)

*These events cover the following: hepatic failure, fibrosis and cirrhosis, and other liver damage-related conditions; non-infectious hepatitis; benign, malignant and unspecified liver neoplasms ULN: upper limit of normal

Table 16-2 Follow up requirements for liver laboratory triggers with liver symptoms

	ALT	TBL	Liver Symptoms	Action
ALT increase without bilirubin increase:				
	If normal at baseline: ALT > 3 x ULN If elevated at baseline: ALT > 2 x baseline or > 300 U/L (whichever occurs first)	Normal For patients with Gilbert's syndrome: No change in baseline TBL	None	
 • No change to study treatment • Measure ALT, AST, ALP, GGT, TBIL, INR, albumin, CK, and GLDH (if available at local laboratory) in 48-72 hours. • Follow-up for symptoms.
	If normal at baseline: ALT > 5 x ULN for more than two weeks If elevated at baseline: ALT > 3 x baseline and > 10x ULN	Normal For patients with Gilbert's syndrome: No change in baseline TBL	None	
	If normal at baseline: ALT > 8 x ULN	Normal	None	
ALT increase with bilirubin increase:				
	If normal at baseline: ALT > 3 x ULN If elevated at baseline: ALT > 2 x baseline	TBL > 2 x ULN For patients with Gilbert's syndrome: Doubling of direct bilirubin	None	
 • Follow-up for symptoms. • Initiate close monitoring and workup for competing etiologies. • Study drug can be restarted only if another etiology is identified and liver enzymes return to baseline.
	If normal at baseline: ALT > 3 x ULN If elevated at baseline: ALT > 2 x baseline	Normal or elevated	Severe fatigue, nausea, vomiting, right upper quadrant pain	

Table 16-3 Follow up requirements for liver laboratory triggers

Criteria	Actions required	Follow-up monitoring
Total Bilirubin (isolated)		
>1.5 – 3.0 ULN	
 • Maintain treatment • Repeat LFTs within 48-72 hours 	Monitor LFTs weekly until resolution to ≤ Grade 1 or to baseline
> 3 - 10 × ULN (in the absence of known Gilbert syndrome)	
 • Interrupt treatment • Repeat LFT within 48-72 hours • Hospitalize if clinically appropriate • Establish causality • Record the AE and contributing factors (e.g. conmeds, med hx, lab) in the appropriate eCRF 	Monitor LFTs weekly until resolution to ≤ Grade 1 or to baseline (ALT, AST, total bilirubin, Alb, PT/INR, ALP and GGT) Test for hemolysis (e.g. reticulocytes, haptoglobin, unconjugated [indirect] bilirubin)
> 10 x ULN	
 • Discontinue the study treatment immediately • Hospitalize the participant • Establish causality • Record the AE and contributing factors(e.g. conmeds, med hx, lab)in the appropriate eCRF 	ALT, AST, total bilirubin, Alb, PT/INR, ALP and GGT until resolution ^a (frequency at investigator discretion)
Any AE potentially indicative of a liver toxicity*	
 • Consider study treatment interruption or discontinuation • Hospitalization if clinically appropriate • Establish causality • Record the AE and contributing factors(e.g., conmeds, med hx, lab)in the appropriate eCRF 	Investigator discretion

*These events cover the following: hepatic failure, fibrosis and cirrhosis, and other liver damage-related conditions; non-infectious hepatitis; benign, malignant and unspecified liver neoplasms ULN: upper limit of normal

^a Resolution is defined as an outcome of one of the following: (1) return to baseline values, (2) stable values at three subsequent monitoring visits at least 2 weeks apart, (3) remain at elevated level after a maximum of 6 months, (4) liver transplantation, and (5) death.

Based on investigator’s discretion investigation(s) for contributing factors for the liver event can include: Serology tests, imaging and pathology assessments, hepatologist’s consultancy; obtaining more detailed history of symptoms and prior or concurrent diseases, history of concomitant drug use, exclusion of underlying liver disease.

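### Table 16-2's combined ALT-and-bilirubin row, which limits restarting study drug, omits AST and the > 300 U/L limb that the protocol's own liver triggers use

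*Protocol*

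**What the plan says.** Section 6.6.2 sends sites to Appendix 1 for stopping or interrupting drug when ALT or AST is raised. Section 9.1.1 requires discontinuation for the liver results specified there.

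Within Appendix 1, Table 16-1 defines the triggers on either enzyme:

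- Potential Hy's Law: "ALT or AST > 3 × ULN and Total bilirubin > 2 × ULN", with further conditions on the bilirubin fraction and ALP.
- Symptomatic: "ALT or AST > 3 × ULN accompanied by (general) malaise, fatigue, abdominal pain, nausea, or vomiting", or rash with eosinophilia.
- Abnormal baseline: "ALT or AST > 2x baseline or > 300 U/L (whichever occurs first").

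Section 6.5.1.1 likewise uses AST or ALT. For an elevated baseline it includes the 300 U/L alternative and requires total bilirubin both > 2 x baseline and > 2 x ULN.

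Table 16-2 holds the transaminase action rows, and its enzyme criteria name ALT only. Row 1 (normal bilirubin, no symptoms) reads "If elevated at baseline: ALT > 2 x baseline or > 300 U/L (whichever occurs first"). The combined and symptomatic rows both read "If normal at baseline: ALT > 3 x ULN If elevated at baseline: ALT > 2 x baseline". The combined row's bilirubin cell is "TBL > 2 x ULN For patients with Gilbert's syndrome: Doubling of direct bilirubin", and its action text includes "Study drug can be restarted only if another etiology is identified and liver enzymes return to baseline". AST appears only among the repeat tests: "Measure ALT, AST, ALP, GGT, TBIL, INR, albumin, CK, and GLDH".

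**The concern.** The table meant to tell a site what to do with study drug is narrower than the definitions that bring a patient to it, and narrower in the cases the protocol treats as most serious. A patient can meet the 6.5.1.1 definition of a potentially severe injury and still not meet the row with the restart condition. Table 16-3 does not fill the gap, because its bilirubin rows are for isolated bilirubin elevation. At stake is whether sites and arms apply the same hold and restart rule to the same liver event. No efficacy inference is involved.

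**Working it through.** The plan gives no figure to reproduce here, so the check sets the rules side by side and passes test cases through them.

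**Step 1. Criteria as written.**

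| Rule | Enzyme | Normal baseline | Elevated baseline | Bilirubin |
|---|---|---|---|---|
| 6.5.1.1 | AST or ALT | > 3 x ULN | > 2 x baseline or > 300 U/L | > 2 x ULN (elevated baseline: also > 2 x baseline) |
| Table 16-1, Hy's Law | ALT or AST | > 3 x ULN | not stated | > 2 x ULN |
| Table 16-1, abnormal baseline | ALT or AST | not applicable | > 2 x baseline or > 300 U/L | none |
| Table 16-2, row 1 | ALT | > 3 x ULN | > 2 x baseline or > 300 U/L | normal |
| Table 16-2, combined | ALT | > 3 x ULN | > 2 x baseline | > 2 x ULN |
| Table 16-2, symptomatic | ALT | > 3 x ULN | > 2 x baseline | normal or elevated |

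(Gilbert's syndrome variants are left out.)

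**Step 2. AST-driven case.** All values are normal at baseline; later AST is 4 x ULN, total bilirubin 2.5 x ULN and ALT normal.

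- 6.5.1.1: 4 > 3 and 2.5 > 2, so it is met. The Hy's Law trigger is also met if the fraction and ALP conditions hold.
- Table 16-2 combined row: it needs ALT > 3 x ULN, so it is not met. No other row of the table names AST as a criterion.

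**Step 3. The > 300 U/L limb.** Assume an ULN of 40 U/L. Baseline ALT is 180 U/L, and 180 / 40 = 4.5 x ULN, below the exclusion limit of 5 x ULN in Section 5.2. Later ALT is 320 U/L, and 320 / 180 = 1.78 x baseline. Bilirubin goes from 0.8 to 2.1 x ULN.

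- 6.5.1.1 enzyme limb: 320 > 300, met. Bilirubin: 2.1 > 2 x 0.8 = 1.6 and 2.1 > 2.0, met.
- Combined row: 2 x 180 = 360 and 320 < 360, not met.
- With bilirubin normal and no symptoms, the same ALT meets row 1, since 320 > 300. The milder picture has a row; the worse one does not.

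**Step 4. How wide that window is.** The limb matters only when 300 < 2 x baseline, so baseline > 300 / 2 = 150 U/L. Taking the screening ALT as baseline, eligibility requires < 5 x ULN.

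| Assumed ULN (U/L) | 5 x ULN | Baseline ALT at which the limb matters |
|---|---|---|
| 30 | 150 | none |
| 35 | 175 | 150-175 |
| 40 | 200 | 150-200 |
| 55 | 275 | 150-275 |

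Within the window, the missed values lie above 300 and up to 2 x baseline: 300-320 U/L at baseline 160, and 300-360 U/L at baseline 180.

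**Step 5. What still applies to these cases.** Section 6.5.1.1 requires diagnostic work-up. For Table 16-1 events, 10.2.1 requires repeat tests and, once the elevation is confirmed, close observation, with interruption or discontinuation if appropriate. Section 9.1.1 obliges the investigator to stop drug when continuing would harm the participant or participation might carry a safety risk. None of the three states an enzyme-based criterion for holding or restarting drug.

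**The case against.** The strongest reply is that these patients are well protected already. Besides the provisions in Step 5, 9.1.1 requires discontinuation for a Grade 4 non-hematologic event attributed to study drug. Section 6.6.2 holds drug for other attributed Grade 3 non-hematologic events, which might capture a bilirubin or jaundice event. In-hospital chemistry runs every two days, so repeat values arrive anyway. A reader who inferred that affected patients go unmonitored, or must stay on drug, would be wrong. This stands and limits the point to the missing criterion; the backstops turn on judgment, attribution or grade.

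A second reply is that row 1 only prescribes monitoring, so a more sensitive threshold there than in a row restricting restart is defensible. That has some force for the 300 U/L limb. It does not explain why AST is absent, or why 6.5.1.1 puts the limb in its own combined definition.

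Two further inferences are tempting. A reader might see a hole for asymptomatic raised ALT with bilirubin above normal but not > 2 x ULN, and want the > 5 x ULN and > 8 x ULN rows widened to take it. The action cells of those rows are not legible in the text reviewed, so neither the harm nor the benefit can be established. A reader might also expect an AST edit to align the symptomatic row fully with Table 16-1. It would not: Table 16-1 includes malaise, fatigue of any degree and rash with eosinophilia, while Table 16-2 requires severe fatigue, nausea, vomiting or right upper quadrant pain. The symptomatic row's own action cell is also not legible, so the case rests on the combined row.

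**Conclusion.** The mismatch is real and minor. The combined row, and likewise the symptomatic row, omits AST for every patient and omits the > 300 U/L limb for patients with elevated baseline ALT. The AST part follows directly from the text. The 300 U/L part is narrow: it needs a baseline ALT between 150 U/L and 5 x ULN, a later value above 300 but not above 2 x baseline, and bilirubin > 2 x ULN (or symptoms, for the symptomatic row). At an ULN of 30 it cannot arise. For an elevated baseline, the case counts as potential liver injury under 6.5.1.1 only if bilirubin has also more than doubled from baseline.

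The ULN values are assumptions, and the documents give no frequency for these events, so this is a statement about rules and not about how many patients are affected. Alpha, power, sample size and the primary analysis are unchanged.

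**What to change.** In Table 16-2, in the combined row and for consistency the symptomatic row:

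1. Change *ALT* to *ALT or AST*.
2. For an elevated baseline, add *or > 300 U/L (whichever occurs first)*, applied to an enzyme that was at or below 300 U/L at baseline. The qualifier is needed because Section 5.2 sets an entry limit for ALT but none for AST; without it, a patient entering with AST above 300 U/L would meet the limb at once.

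Leave the bilirubin criteria and the other rows as they are.

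The cost is an appendix edit in the next amendment and a notice to sites. No tests are added: Section 8.4.1 already schedules ALT, AST, total bilirubin and creatine kinase. The downside is a few extra holds for AST rises of non-hepatic origin, which the scheduled creatine kinase helps identify.

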16.2 Appendix 2: Clinical status 9-point scale

Clinical status (9-point ordinal scale):

Patient State	Descriptor	Score
Uninfected	No clinical or virological evidence of infection	0
Ambulatory (defined as not in hospital or in hospital and ready for discharge)	No limitation of activities	1
	Limitation of activities	2
Hospitalized Mild Disease	Hospitalized, no oxygen therapy (defined as SpO ₂ ≥ 94% on room air)	3
	Oxygen by mask or nasal prongs	4
Hospitalized Severe Disease	Non-invasive ventilation or high-flow oxygen	5
	Intubation and mechanical ventilation	6
	Ventilation + additional organ support – pressors, RRT (renal replacement therapy), ECMO (extracorporeal membrane oxygenation)	7
Dead	Death	8

Reference: WHO (18-Feb-2020). WHO R&D Blueprint. Novel coronavirus. COVID-19 Therapeutic Trial Synopsis (Dated 18-Feb-2020).

16.3 Appendix 3: National Early Warning Score 2 (NEWS2)

Physiological parameter	Score						
	3	2	1	0	1	2	3
Respiration rate (per minute)	≤8		9–11	12–20		21–24	≥25
SpO ₂ Scale 1 (%)	≤91	92–93	94–95	≥96			
SpO ₂ Scale 2 (%)	≤83	84–85	86–87	88–92 ≥93 on air	93–94 on oxygen	95–96 on oxygen	≥97 on oxygen
Air or oxygen?		Oxygen		Air			
Systolic blood pressure (mmHg)	≤90	91–100	101–110	111–219			≥220
Pulse (per minute)	≤40		41–50	51–90	91–110	111–130	≥131
Consciousness				Alert			CVPU
Temperature (°C)	≤35.0		35.1–36.0	36.1–38.0	38.1–39.0	≥39.1	

SpO₂ = oxygen saturation.

The oxygen saturation should be scored according to either the SpO₂ Scale 1 or 2 presented in the table above. The SpO₂ Scale 2 is for patients with a target oxygen saturation requirement of 88%-92% (e.g., in patients with hypercapnic respiratory failure related to advanced lung diseases, such as chronic obstructive pulmonary disease [COPD]). This should only be used in patients confirmed to have hypercapnic respiratory failure by blood gas analysis on either a prior or their current hospital admission.

The decision to use the SpO₂ Scale 2 should be made by the treating physician and should be recorded in the eCRF. In all other circumstances, the SpO₂ Scale 1 should be used.

For physiological parameter “Air or Oxygen?”: Any patients requiring the use of oxygen or other forms of ventilation to maintain oxygen saturations and support respiration should be assigned a score of 2.

The consciousness level should be recorded according to the best clinical condition of the patient during the assessment. Patients who are assessed as “Alert” (A) should be assigned a score of 0. Patients assessed as “New Confusion” (C), “Responsive to Voice” (V), “Responsive to Pain” (P), or “Unconscious” should be assigned a score of 3.

Scores should be assigned for respiratory rate, systolic blood pressure, pulse, and temperature according to the table above.

NEWS2 values will be calculated electronically throughout the study by the Sponsor based upon entry of vital sign parameters by the investigator in the appropriate eCRF.

Example Case Calculation:

An 82-year-old lady was admitted, tested positive to COVID-19 and admitted to high dependency unit for non-invasive ventilation. Her taken observations and corresponding NEWS2 score are as follows:

Physiological Parameter	Observation	Component Score
Respiratory rate (per min)	26	3
Oxygen saturation (SpO ₂ %)	95%	1
Supplemental Oxygen	Yes	2
Systolic blood pressure (mmHg)	95	2
Pulse Rate (bpm)	109	1
Conscious level	New confusion	3
Temperature (°C)	39	1
	Total NEWS2 Score	13

Reference:

Royal College of Physicians. National Early Warning Score (NEWS) 2: Standardising the assessment of acute-illness severity in the NHS. Updated report of a working party. London: RCP, 2017.

16.4 Appendix 4: List of CYP3A4 inhibitors and inducers

Table 16-4 CYP3A4 inhibitors and inducers

Dual CYP2C9/CYP3A4 inhibitor:

Fluconazole: Avoid the concomitant use of ruxolitinib with fluconazole doses ≥ 200 mg daily; If clinically necessary to use doses ≥ 200 mg daily consultation with Sponsor is required. Please refer to [Section 6.2](#).

Category	Drug Names
Strong inhibitors ^a of CYP3A	boceprevir, clarithromycin, cobicistat, conivaptan, danoprevir/ritonavir, eltegravir/ritonavir, grapefruit juice ¹ , idelalisib, indinavir, itraconazole, ketoconazole, lopinavir/ritonavir, LCL161, mibefradil, nefazodone, nelfinavir, posaconazole, ritonavir, saquinavir, sequinavir/ritonavir, telaprevir, telithromycin, voriconazole, indinavir/ritonavir, tipranoavir/ritonavir, troleandomycin,
Moderate inhibitors ^b of CYP3A	amprenavir, aprepitant, atazanavir, atazanavir/ritonavir,, casopitant, cimetidine, ciprofloxacin, crizotinib, cyclosporin, duranavir, darunavir/ritonavir, diltiazem, dronedarone, erythromycin, faldaprevilr, fluconazole ² , fosamprenavir, grapefruit juice ¹ , imatinib, lomitapide, netupitant, nilotinib, schisandra sphenanthera ³ , tofisopam, verapamil
Strong inducers ^c of CYP3A	avasimibe, carbamazepine, enzalutamide, mitotane, phenytoin, rifampin, St. John's wort ³ , rifabutin, phenobarbital,
Moderate inducers ^d of CYP3A	bosentan, efavirenz, etravirine, genistein ³ , lersivirine, lopinavir, modafinil, nafcillin, ritonavir, semagacestat ⁴ , talviraline ⁴ , thioridazine, tipranavir,

The list of CYP inhibitors and inducers was compiled from the FDA's "Guidance for Industry, Drug Interaction Studies;" from the Indiana University School of Medicine's "Clinically Relevant" Table and from the University of Washington's Drug Interaction Database. Note that this may not be an exhaustive list. For a complete and most updated drug list, please check the website <https://crediblemeds.org/healthcareproviders/drug-list>.

¹ Effect seems to be due to CYP2C19 inhibition by ethinyl estradiol.

² Fluconazole is a dual CYP3A4 and CYP2C9 inhibitor. Fluconazole is a strong CYP2C9 inhibitor based on the AUC ratio of omeprazole, which is also metabolized by CYP3A; fluconazole is a moderate CYP3A inhibitor.

³ Herbal product.

⁴ Drugs not available in the US Market.

a. A strong inhibitor for a specific CYP is defined as an inhibitor that increases the AUC of a sensitive substrate for that CYP by equal or more than 5-fold.

b. A moderate inhibitor for a specific CYP is defined as an inhibitor that increases the AUC of a sensitive substrate for that CYP by less than 5-fold but equal to or more than 2-fold

- c. A strong inducer for a specific CYP is defined as an inducer that decreases the AUC of a sensitive substrate for that CYP by equal or more than 80%.
- d. A moderate inducer for a specific CYP is defined as an inducer that decreases the AUC of a substrate for that CYP by 50-80%.
